Short-term Effects of Intravenous Dexketoprofen Trometamol and Tramadol on Perfusion-Related Physiological Parameters in Renal Colic

Short-term Perfusion Effects: Dexketoprofen/Tramadol

METHODS

Study design and setting

This single-centre, prospective, randomised study was conducted in the emergency department of Ataturk University Research and Training Hospital between November 2024 and April 2025. Adult patients aged 18–55 years presenting with flank pain and diagnosed with renal colic based on clinical evaluation and appropriate imaging were screened for eligibility.

Participants

Patients who met the inclusion criteria were required to have a Glasgow Coma Scale score of 15, spontaneous respiration, and the capacity to provide informed consent. Exclusion criteria encompassed pregnancy or breastfeeding, chronic kidney disease, known allergy to study medications, chronic respiratory disease, hemodynamic instability, acute intoxication, uncontrolled epilepsy, or recent monoamine oxidase inhibitor use.

Randomisation and interventions

Participants were randomly assigned to one of three groups in a 1:1:1 ratio, receiving intravenous dexketoprofen trometamol (50 mg), tramadol (100 mg), or a combination of dexketoprofen trometamol (50 mg) and tramadol (50 mg). All medications were diluted in 100 mL of normal saline and administered intravenously. The administration of rescue analgesia in the form of intravenous morphine (5 mg) was permitted at the discretion of the treating physician.

Data collection and monitoring

Physiological variables, including blood pressure, heart rate, oxygen saturation, respiratory rate, and EtCO₂, were recorded at baseline (T0), 30 minutes (T30), and 60 minutes (T60). Arterial blood-gas analysis was performed at T0 and T60. The primary outcome of the study was a change in EtCO₂ over time, while secondary outcomes included changes in vital signs and blood-gas parameters.

The primary outcome was the change in EtCO₂ over time (T0, T30, T60) and the comparison of these changes between the three analgesic groups as a surrogate marker of global tissue perfusion. Secondary outcomes encompassed the trajectories of heart rate, blood pressure and SpO₂ over time; changes in arterial blood gas parameters (pH, bicarbonate, PaCO₂, lactate and

base deficit) between T0 and T60; and comparison of these physiological responses across treatment groups.

Sample size and statistical analysis

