Sample size was calculated in G*Power using previously published data on EtCO₂ changes after tramadol or oxycodone administration (16). With $\alpha = 0.05$ and 80% power, 34 patients per group (102 in total) were required.

The analysis of the data was conducted utilising the SPSS version 25.0 software. The assessment of normality was conducted through histogram inspection and the implementation of the Shapiro–Wilk test. Continuous variables are presented as mean \pm standard deviation or change over time, and categorical variables as counts and percentages. The alterations in vital signs and blood-gas variables occurring within and between the groups were subjected to analysis using repeated-measures ANOVA. For the purpose of comparing the between-group alterations, one-way ANOVA with Tukey post hoc tests were employed. Paired t tests were utilised for within-group comparisons between T0 and T60, and χ^2 tests were used for the analysis of categorical variables. Statistically speaking, a p value of less than 0.05 was deemed to be significant.

Ethics Approval

The study was approved by the Erzincan Binali Yıldırım University Clinical Research Ethics Committee (Decision No. 2024-16/01, 07 Nov 2024) and conducted in accordance with the Declaration of Helsinki. All participants provided written informed consent.

CRediT authorship contribution statement

[name]: Conceptualization, Data curation, Formal analysis, Investigation, Methodology, Resources, Software.

[name]: Conceptualization, Formal analysis, Investigation, Methodology, Resources, Supervision, Validation, Visualization, Writing – original draft, Writing – review & editing.

Declaration of Competing Interest

The authors declare that they have no competing financial interests or personal relationships that could have influenced the work reported in this paper.

Data availability statement

The data that support the findings of this study are not publicly available due to privacy and ethical restrictions, as they contain identifiable patient information.

Funding Statement

No funding

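### The between-group EtCO₂ comparison leaves out T0 as a covariate: a valid analysis that forgoes a nearly cost-free and usually positive gain in precision

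*Combined protocol and SAP*

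**What the plan says.** Under Data collection and monitoring, the primary outcome covers EtCO₂ change and "the comparison of these changes between the three analgesic groups". EtCO₂ is among the variables measured at all three times ("recorded at baseline (T0), 30 minutes (T30), and 60 minutes (T60"). For the blood gases, "Arterial blood-gas analysis was performed at T0 and T60".

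Under Sample size and statistical analysis, changes in vital signs and blood gases within and between groups "were subjected to analysis using repeated-measures ANOVA". The next sentence reads: "For the purpose of comparing the between-group alterations, one-way ANOVA with Tukey post hoc tests were employed". Paired t tests are for within-group comparisons only, and "a p value of less than 0.05 was deemed to be significant". On size, "34 patients per group (102 in total) were required" at α = 0.05 and 80% power.

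No covariate, ANCOVA or other adjustment for T0 is named anywhere. The analysis paragraph does not mention EtCO₂ by name. That these ANOVAs cover it is inferred from the primary outcome, because no other between-group method for a continuous variable is described.

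**The concern.** The plan does use T0, but only by subtraction or as one level of the repeated measure. Subtraction fixes the slope of follow-up EtCO₂ on T0 EtCO₂ at exactly 1. ANCOVA estimates that slope from the data. When the true slope is below 1, which is common for a physiological variable measured twice, the change score carries T0 noise that adjustment would remove. Repeated-measures ANOVA does not close the gap, since its group×time test also compares changes with no T0 covariate.

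Precision is what is at stake. The trial has 34 patients per arm, is sized for only 80% power, and compares three arms pairwise. T0 is already recorded, so adjusting for it needs no new data.

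**Working it through.** **Inputs from the documents.** Three groups randomised 1:1:1, 34 per group (102 in total), α = 0.05, power 80%, EtCO₂ at T0, T30 and T60.

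**Assumptions, because the documents are silent.** The T0–T60 correlation ρ, the SDs, the effect size, and the test behind the sample size.

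**1. The plan's own figure.** The 34 per group cannot be reproduced without an effect size, so I back-solved it. For a three-group one-way ANOVA (df 2, 99), 80% power needs noncentrality λ = 102 × f² = 9.93, so f = 0.312. A two-sided two-group t test with d = 0.69 fits 34 equally well. So does a repeated-measures interaction with f of about 0.20 to 0.11 (ρ from 0 to 0.7). The steps below assume one-way ANOVA on T60−T0 change.

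**2. Variance ratio, common slope.** Let s₀ and s₁ be the T0 and T60 SDs.
- Change score: s₀² + s₁² − 2ρs₀s₁
- ANCOVA residual: s₁²(1 − ρ²)
- Difference: (s₀ − ρs₁)², which is never negative and is zero only when ρ × s₁/s₀ = 1

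With equal SDs the ratio of ANCOVA to change-score variance is (1 + ρ)/2.

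**3. Cost of the covariate.** One residual df (99 to 98) and a variance factor of 1 + 1/(102 − 3 − 2) = 1 + 1/97 = 1.01. If the ratio in step 2 is exactly 1, power falls from 80.0% to 79.6%, a loss of 0.4 points.

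**4. Equal SDs, both costs included.** Adjusted power uses λ = 9.93 / (ratio × 1.01) on df 2, 98. At ρ = 0.5, for example, 9.93 / (0.75 × 1.0103) = 13.11, which gives 90.1%. In the last column the variance factor is 1 + 1/(3n − 5) for n per group.

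| ρ | (1 + ρ)/2 | with cost | adjusted power | n per group for 80% |
|---|---|---|---|---|
| 0.3 | 0.65 | 0.66 | 93.9% | 23 |
| 0.5 | 0.75 | 0.76 | 90.1% | 27 |
| 0.7 | 0.85 | 0.86 | 86.0% | 30 |
| 0.8 | 0.90 | 0.91 | 83.8% | 32 |
| 0.9 | 0.95 | 0.96 | 81.7% | 33 |

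At ρ = 0.98 the ratio with cost is 1.00 and the gain is gone. Simulation with 34 per group gave variance ratios of 0.66, 0.76, 0.86 and 0.96 at ρ = 0.3, 0.5, 0.7 and 0.9, in agreement with the table.

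**5. Unequal SDs.** With T60 SD 1.25 times T0 SD, the ratio before cost is 0.78, 0.89, 0.98, 1.00 and 0.95 for the same five values of ρ. At ρ = 0.8, ρ × 1.25 = 1 and nothing is gained.

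**6. Slopes that differ between arms.** Take T0 SD 1, residual SD 0.6 (variance 0.36) and true slopes 0.9, 0.9 and 0.3. The pooled slope is about 0.7.
- Contrast of the two similar arms: per-arm variance is 0.36 + (0.9 − 1)² = 0.37 for change and 0.36 + (0.9 − 0.7)² = 0.40 for pooled ANCOVA. The ratio is 1.08 in large samples, and 1.08 to 1.11 in simulations at 34 per group.
- Either contrast with the third arm: 0.37 + 0.36 + (0.3 − 1)² = 1.22 for change, and 0.40 + 0.36 + (0.3 − 0.7)² = 0.92 for ANCOVA. The ratio is 0.75.

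With milder differences (0.8, 0.8, 0.5) the similar-arm contrast still gains, with a ratio of 0.93.

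**The case against.** The strongest reply is that nothing here is wrong. Randomisation makes the change-score comparison unbiased, the primary outcome is itself defined as a change, and one-way ANOVA on changes matches that definition directly. This stands, and it limits the point to efficiency. A reader might infer from the missing covariate that the planned result is biased or invalid. The documents do not support that.

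A reader might also infer that ANCOVA can never be less precise. That needs a common T0 slope. Step 6 shows that a pooled slope can cost one contrast roughly 10% in variance while the other two gain. Only strong slope differences do this, and arm-specific slopes avoid it.

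A third temptation is to go further and make a T30/T60 average the primary test. That changes what is estimated and is not a free gain. If the effect grows linearly to T60 (averaged effect 0.75 of the T60 effect) with equal SDs and equal correlations between times, the adjusted average has variance (1 + 2ρ)/4 of the T60 change. Its power is then about 77, 74 and 70% at ρ = 0.7, 0.8 and 0.9, below the 80% of the plain T60 change. The documents do not say how the effect is expected to develop, so they give no ground for that switch.

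Finally, the trial ran "between November 2024 and April 2025" and its analysis is described in the past tense. If outcomes have been seen, adjustment cannot add power to the primary test. That also stands, and the fix allows for it.

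**Conclusion.** The point holds as a missed gain in precision. T0 EtCO₂ is collected and the between-group analysis does not adjust for it. With a common slope the downside is bounded at about 1% in variance (0.4 power points). The upside ranges from near nil to a variance reduction of about a third at ρ = 0.3 with equal SDs, which would take power from 80% to 93.9%.

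The direction of the result rests on algebra. Its size rests on assumed ρ and SDs and on the assumption that 34 per group came from one-way ANOVA on T60−T0 change, none of which the documents state. The power figures therefore show a plausible range and do not estimate this trial's loss. They also do not show that 34 per group was too few.

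**What to change.** Keep the planned time points and comparisons, and add T0 EtCO₂ as a covariate to the between-group analysis. Either of these would do:
- ANCOVA of follow-up EtCO₂ on group and T0.
- A mixed model on T30 and T60 with group, time, group×time, T0 and T0×time.

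Report Tukey-adjusted pairwise differences with 95% CIs. Check group×T0. If slopes clearly differ, centre T0 and allow arm-specific slopes. Adjust the T60 blood-gas variables for their own T0 values in the same way. Do not replace the outcome by a T30/T60 average as part of this change.

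If outcomes have already been examined, report the planned ANOVA as primary and the T0-adjusted result beside it, labelled post hoc.

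The cost is one re-run of the analysis in SPSS, which is already in use and has the procedures (UNIANOVA, MIXED). No patients or measurements are added.

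### With three arms, a step-down form of the planned Tukey tests would keep the 5% family-wise error, lose no Tukey finding and add power for the second and third pairs: a cheap improvement, not a correction

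*Combined protocol and SAP*

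**What the plan says.** The section on randomisation and interventions states: "Participants were randomly assigned to one of three groups in a 1:1:1 ratio". There are therefore three pairwise comparisons. The section on data collection and monitoring makes "the comparison of these changes between the three analgesic groups" part of the primary outcome, EtCO₂ change.

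The section on sample size and statistical analysis lists repeated-measures ANOVA for changes within and between groups. For comparing the between-group changes it adds that "one-way ANOVA with Tukey post hoc tests were employed". The threshold is that "a p value of less than 0.05 was deemed to be significant". The planned size is given as "80% power, 34 patients per group (102 in total) were required".

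No effect size, SD, step-down or closed procedure, or simultaneous confidence interval is mentioned. The plan also does not say whether the Tukey tests are run only after a significant F test.

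**The concern.** Single-step Tukey applies the same strict critical value to all three pairs, whatever the other pairs show. With exactly three arms this is more caution than family-wise control needs. Once equality of all three arms has been rejected, at most one pair can still be truly equal, so the remaining pairs can be tested at the ordinary 5% level.

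What is at stake is which regimens are separated from which. If one regimen stands apart from two similar ones, Tukey may declare only one of the two real differences. Under the assumption of a 0.69 SD separation this happens in about 29% of trials; at 1.0 SD it happens in about 6.5%.

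**Working it through.** **Inputs from the document.** Three arms, 1:1:1; 34 per arm, 102 in total; α = 0.05, taken as two-sided because sidedness is not stated. Error degrees of freedom: 102 − 3 = 99.

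**The plan's own figure.** The 34 per group cannot be reproduced, because neither the effect size nor the test family is given. Solved backwards at 80% power, 34 per group corresponds to d = 0.69 for a two-sided two-sample t test, d = 0.61 for a one-sided one, or f = 0.312 for a three-group one-way ANOVA. I use 0.69 SD as one illustrative effect among several.

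**Critical values.** Tukey: q(0.95; 3, 99)/√2 = 3.365/√2 = 2.379, a two-sided per-pair level of 1.93% (1.91% to 1.93% for any size of 30 or more per arm). Unadjusted: |t| > 1.984. With standard error √(2/34) = 0.2425 SD, the smallest observed difference that counts is 2.379 × 0.2425 = 0.577 SD under Tukey, against 1.984 × 0.2425 = 0.481 SD unadjusted.

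**Step-down rule.** If the largest |t| exceeds 2.379, declare every pair with |t| > 1.984; otherwise declare none. Hypothetical example: pairwise t values of 2.6, 2.1 and 0.5. Tukey declares only the first pair; the step-down declares the first two.

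**Family-wise error.** With three means, any two true equalities imply the third, so there are three cases.
- All arms equal: an error requires the largest |t| to exceed 2.379, which has probability 5%.
- Exactly one pair equal: an error requires that pair's |t| to exceed 1.984, so at most 5%.
- No pair equal: no false rejection is possible.

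**No Tukey rejection is lost.** A pair beyond 2.379 opens the gate and itself exceeds 1.984. Simulation found no losses in any run.

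**Power.** Simulation with 34 analysed per arm, normal data, common SD and 400,000 trials per scenario. The means are assumptions, in SD units, and the baseline is Tukey without a preceding F gate.

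| Means | Target | Tukey | Step-down |
|---|---|---|---|
| 0, 0, 0.69 | one real pair | 67.9% | 74.9% |
| 0, 0, 0.69 | both real pairs | 53.3% | 67.3% |
| 0, 0, 0.783 | one real pair | 80.0% | 85.9% |
| 0, 0, 0.783 | both real pairs | 68.8% | 80.6% |
| 0, 0.7, 1.4 | adjacent pair | 69.3% | 81.6% |
| 0, 0.7, 1.4 | all three pairs | 42.8% | 63.9% |

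With one arm apart, the gains peak near 0.6 SD (about 7 points per pair and 14 for both) and fall to about 2 and 4 points at 1.0 SD. For the extreme pair of equally spaced arms the gain is only about 0 to 2 points. The chance of at least one significant pair is identical, since both rules start with the same test.

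**Error on a truly equal pair.** With all arms equal, family-wise error is 4.96% for both rules. With one arm apart, the chance of falsely separating the two equal arms is about 1.9% under Tukey. Under the step-down it is 3.4% at 0.3 SD, 4.9% at 0.69 SD and 5.0% for larger separations.

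**The case against.** Tukey for three equal-sized arms is a standard choice that holds its 5% level, so preferring another valid procedure may look like taste. It stands that nothing here is wrong. A reader might infer that the planned tests are invalid, but the documents do not support that. The suggestion goes beyond taste because the alternative keeps every Tukey rejection, and the plan mentions no simultaneous intervals that would have to be given up.

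A reader might also infer that the trial has only 68% power instead of the stated 80%. That would require knowing that 34 per group was sized for a pairwise t test at 0.69 SD. The document says only "Sample size was calculated in G*Power using previously published data on" EtCO₂ changes and gives neither the effect nor the test.

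The unused allowance under Tukey has some value. The 5% guarantee covers one contrast on one outcome, while the plan has several vital signs and five blood-gas variables with no correction across them. The benefit also depends on the effect. At 0.69 SD the fully correct pattern (both real differences declared, the equal pair not) rises from 52.9% to 65.2%, but at 1.2 SD it falls from 97.2% to 94.8%. Both points stand as costs to disclose.

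The plan does not say that the Tukey tests decide the primary outcome, since repeated-measures ANOVA is listed as well. The gain is therefore confined to the pairwise statements. If Tukey was meant only after a significant F test, it is tempting to treat F-gated unadjusted tests as the same remedy. They also hold 5% with three arms, but they are a different rule. Their rejections differ from the step-down's in up to 3.5% of simulated trials and miss an ungated Tukey rejection in up to 1.5%. They dominate only F-gated Tukey.

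The strongest objection is timing. The section on study design and setting describes the study in the past tense, running to April 2025. Adopting a rule that can only add significant pairs after seeing results would be a post hoc loosening. This stands and limits when the change can be made.

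**Conclusion.** The planned single-step Tukey tests are valid but less powerful than three arms require. A step-down form holds family-wise error at or below 5% for a given outcome and contrast and never loses a Tukey rejection. Both follow from the logic of three means and do not depend on any assumed effect.

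The size of the gain does depend on assumed effects, 34 analysed per arm, normality and a common SD. It is about 7 points per real pair and 14 for both when one arm lies 0.69 SD from two equal arms. It is about 12 points for an adjacent pair and 21 for all three when arms are spaced 0.7 SD apart. Neither set of figures is a general bound, and the gain shrinks for large effects. It falls wholly on the second and third comparisons. This is an optional, inexpensive improvement to consider.

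**What to change.** Add one sentence to the statistical analysis section, for example: *For each pair of arms the adjusted p value is the larger of its unadjusted pooled-error p value and the smallest of the three Tukey p values; the pair is declared different if this is below 0.05.* Any Tukey intervals may be reported alongside.

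The cost is that sentence, with no extra patients or data. Two downsides should be stated with it. The chance of falsely separating two truly equal arms rises from 1.9% to as much as 5%, still inside the family-wise limit. A declared pair's Tukey interval may include zero, which needs a footnote.

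The rule must be fixed before results are seen. If they have been seen already, keep Tukey as the pre-stated verdict and label the step-down p values as added later. The section should also state whether Tukey is conditional on a significant F test.
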